	evaluate the tolerability of a combination thera amin D in children and adolescents newly diag					
EDCR IIa						
Investigators and Study Centre:						
Approximately 9 sites in Sweden, in	cluding approximately 20 patients.					
Phase of Development: Phase IIa						
Objectives:						
	a combination therapy with Diamyd, vitamin a combination therapy with Diamyd, vitamin a continue the treatments influence the immune system of the system of					
Study Design:						
	el, pilot clinical trial. All patients will from Da	ay 1 receive 2 000 IU				
vitamin D per os per day during 15 i	nonths, and from Days 1-90 receive etanercep	t (Enbrel) injected				
subcutaneously 0.8 mg/kg body wei	ght (max 50 mg) once a week, and receive 2 st	ubcutaneous injections of				
	regimen on Days 30 and 60. The patients will					
	period, 6 visits) and followed for additionally	y 24 months (extension				
study period, 3 visits). The total stu-						
	st be age 8.00 to 17.99 years old, and diagnose					
	at the time of screening. Patients will be eligib					
	mL) and elevated levels of GAD65 antibodies	are present.				
U	proximately 20 patients will be enrolled.					
Description of Treatment Groups						
	The patients will be assessed for eligibility at					
	1) 2 to 4 weeks prior to the start of the treatment. On Visit 2 (Day 1), patients eligible for the study will start					
the treatment as mentioned above.						

Name of Sponsor [name] Name of Finished Product: DIAMYD [®] ETANERCEPT VITAMIN D	Individual Study Table Referring to Part of Dossier in Which the Individual Study or Study Table is Presented:	(For National Authority Use Only)
Name of Active Ingredient: Recombinant Human Glutamic Acid Decarboxylase (rhGAD65) Calciferol (Vitamin D) Etanercept	Volume: Reference:	

Endpoints

Primary endpoints:

To Evaluate the tolerability of a combination therapy with Diamyd, Vitamin D and etanercept at Month 6 (main study Period), 9, 15 and 30 (extension study period)

Variables to evaluate tolerability:

- Reactions at the injection site
- Infections
- Occurrence of Adverse Events (AEs)
- Occurrence of Serious Adverse Events
- Physiological and Neurology assessments
- Laboratory measurements (biochemistry and haematology), including Calcium and Vitamin D in serum
- GAD65AB titer (GADA)

Secondary endpoints:

To evaluate how the above mentioned treatments influence the immune system and endogenous insulin secretion at Month 6 (main study Period), 9, 15 and 30 (extension study period)

Variables to evaluate the influence on the immune system:

- Inflammatory markers, especially TNF-alfa, IL-1 beta, IL-2, IL-17
- Th2-deviation of cell-mediated immune response seen e.g. as increased ratio of IL-5,10, 13 in comparison with IFN-gamma, TNF-alfa, IL-1 beta and IL-17
- Increase of T-regulatory cells

Variables to evaluate the effect of endogenous insulin secretion:

- C-peptide (90 minute value and AUC_{mean 0-120 min}) during an MMTT
- Proportion of patients with a stimulated maximum C-peptide level above 0.2 nmol/L
- Fasting C-peptide
- Hemoglobin A1c (HbA1c)
- Exogenous insulin dose per kg body weight and 24 hours

Sample size:

No real sample size calculation is done as this is an open-label pilot study just to see if the treatment is tolerable and does not cause negative effects on beta cell function and/or immune system.

All variables will be summarized descriptively

LIST OF ABBREVIATIONS AND DEFINITION OF STUDY SPECIFIC TERMINOLOGY

ADA	American Diabetes Association
AE	Adverse Event
Alum	Aluminum hydroxide
AUC	Area Under the Curve
AUC _{mean 0-120 min}	AUC mean 0-120 minutes
BMI	Body Mass Index
CRF	Case Report Form
CRA	Clinical Research Associate
CRO	Contract Research Organization
DCCT	Diabetes Control and Complications Trial
DCF	Data Clarification Form
DSMB	Data Safety Monitoring Board
EC	Ethics Committee
GAD	Glutamic acid decarboxylase
GADA	Antibodies to GAD with molecular mass 65,000
GAD65	GAD with molecular mass 65,000
GCP	Good Clinical Practice
HbA1c	Hemoglobin A1c
HLA	Human Leukocyte Antigen
IAA	Insulin Autoantibody
IA2	Islet cell Antigen 512
ICH	International Conference on Harmonization
ITT	Intent-to-Treat
LADA	Latent Autoimmune Diabetes in Adults
MMTT	Mixed Meal Tolerance Test
NOD	Non-obese Diabetic
PP	Per-Protocol
rhGAD65	Recombinant Human GAD with molecular mass 65,000
SAP	Statistical Analysis Plan
SAE	Serious Adverse Event
T1D	Type 1 Diabetes
T2D	Type 2 Diabetes

1 Introduction

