2.3 Risks of Etanercept (Enbrel[®])

Etanercept (Enbrel[®]) is one of the clinically most well-used biologics in the world and is regarded as justified in the treatment of Juvenile Idiopathic Arthritis (JIA) also in children down to 2 years of age.

Etanercept has documented side effects and the most commonly reported side effects are injection site reactions, infections (URI, bronchitis, cystitis and skin infections, reactivation of tuberculosis and other serious infections such as tuberculosis, and opportunistic infections, including invasive fungal infections, listeriosis and legionellosis), allergic reactions, development of autoantibodies, itching, pruritus and fever.

TNF blockers such as etanercept affect the immune system and its use can affect the body's immune response towards infections. Serious infections affect less than 1 of 100 patients that are treated with etanercept. Deadly and life-threatening infections as well as sepsis have been reported. Different kinds of malignancies have also been reported while treated with etanercept,

even if this AE has been questioned by Swedish researchers as the incidence of malignancy in children and adults with rheumatic disorders is increased even without treatment. Additionally hematological, neurological and autoimmune reactions have been reported, including rare cases of pancytopenia (less than 1 of 1000) and very rare cases of aplastic anemia (less than one of 10 000). Central and peripheral demyelination has been reported in both rare and very rare cases. Also, rare cases of lupus and lupus-like syndrome and vasculitis have been reported

There are also reports that the risk for hypoglycemia may increase in patients with diabetes being treated with etanercept.

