Our primary aim of the present pilot study is to ensure the combination of etanercept, Vitamin D and GAD-alum is tolerable in children newly diagnosed with T1D. Secondly we want to study how this regimen influences the immune system, block TFN-alfa, and other dangerous cytokines but rather cause the desired Th-2 deviation, increase of T-regulatory cells, and hopefully preservation of residual beta cell function although we do not expect to show statistically convincing proof with this small pilot group of patients in an open trial.

A third aim is to receive more information on how GAD-alum could be combined with other types of treatment to improve efficacy without unacceptable non-justified risk of adverse events.

Thus we want to evaluate the tolerability of a combination therapy of GAD-alum, vitamin D in rather large dose and etanercept given in the same dose as used in the treatment of arthritis also in children.

Based on the results of this open pilot study we then want to use this knowledge for design of a larger Phase II trial to get more robust information. The main long-term goal is then to find a treatment at onset of T1D in young patients which is easy to administer at any clinical setting, tolerable for the patients, reasonably safe, and which can preserve residual insulin secretion and give the patients a better quality of life, with less acute complications and in the long run less risk of late complications.

4 **Objectives and Endpoints**

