6.1 Study Design and Treatment

The trial is multicenter, open-label, pilot study in GADA positive T1D patients of either gender, 8.00 to 17.99 years old, diagnosed with T1D within 100 days at time of screening (Visit 1) and fasting C-peptide levels equal to or above 0.12 nmol/L. In total, approximately 20 patients will be recruited at approximately 10 sites in Sweden.

The patients will be assessed for eligibility at the screening visit (Visit 1) 10 to 21 days prior to the start of treatment. At each site, the screened patients will be assigned a sequential screening number (starting with 01) and this screening number together with the site number will be used as patient identification throughout the study (i.e. XX-XX).

Patients who qualify for inclusion in the study will then be enrolled in the study to receive investigational study drug at the subsequent visits according to table 1 below.

The patients will be followed for a total study period of 30 months which includes 9 visits to the site.

See table 1 below for an overview of the study visits.

Table 1. Study Visits

EDCR IIa	Screening	Intervention – Main Study Period					Follow-up Period	Study	
	Day -10 to -21 Screening	Day 1 Base- line	Day 30 Month 1	Day 60 Month 2	Day 90 Month 3	Day 180 Month 6	Day 270 Month 9	Day 450 Month 15	Day 900 Month 30
	Visit 1	Visit 2	Visit 3 ± 3	Visit 4 ± 3	Visit 5 ± 7	Visit 6 ± 7	Visit 7 ± 14	Visit 8 ± 14	Visit 9 ± 14
Appr 20 subjects		Vitamin I	Vitamin D 2 000 IU daily, from Day 1 to Day 450						
		Etanercept injections once weekly from Day 1 to 90							
			Prime injection GAD- Alum 20 μg	Boost injection GAD- Alum 20 μg					

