10.1 Study Design

The EDCR IIa study is an open controlled pilot intervention trial of the safety, and evaluation of the immune system response and residual insulin secretion, by a combined treatment with etanercept, Vitamin D and GAD-Alum (Diamyd).

Study Participants:

Newly diagnosed classic type 1 diabetes patients: N=20. Age 8.00-17.99 years. Recruited from approximately 10 pediatric clinics in Sweden

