10.2 Estimation of Sample Size

Power analysis:

No formal power analyses is done for this pilot study

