10.3 Statistical Analysis Plan

In brief the following analysis is planned:

All continuous variables will have the following descriptive statistics displayed: number of observations (n), mean value, standard deviation, minimum, median, and maximum. All variables Confidential

of a categorical nature will be displayed with frequencies and percentages. The tabulation of the descriptive statistics will be split by treatment group and visit. Where appropriate, baseline (screening) descriptive statistics will also be included.

Demographic and other baseline characteristics

Demographics such as age and gender will be described for Intention-to-treat and the Total population. Measures for other baseline characteristics are medical history, current medical conditions (at baseline), and current diabetes medication (at baseline). The baseline characteristics will be presented for the safety population. Demographics and baseline characteristics will be presented using descriptive statistics (summary tables).

Variables:

The AE/SAE data will be presented using a standardized tabulation of the frequency and incidence rate of all observed AEs/SAEs. The frequencies and incidence rates are calculated on a per patient basis. Adverse events will be summarized by body system, causality, and severity. Other safety data will be presented by descriptive statistics. Data regarding C-peptide and immune system as well as Adverse events and other safety data will be summarized descriptively.

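### Tolerability is the primary endpoint, yet per-patient adverse event proportions in about 20 patients carry no interval: zero events of a given type is compatible with a true rate up to 16.8%

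*Combined protocol and SAP*

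**What the plan says.** - **Aim.** Section 3 states: "Our primary aim of the present pilot study is to ensure the combination of etanercept, Vitamin D and GAD-alum is tolerable in children newly diagnosed". The same section says the results will feed the design of a larger Phase II trial. Section 4.1 words the formal objective as evaluating tolerability, and Section 4.2.1 makes tolerability the primary endpoint. The variables listed there include injection-site reactions, infections, adverse events and serious adverse events.
- **Size.** Section 6.1: "In total, approximately 20 patients will be recruited at approximately 10 sites in Sweden". Section 10.1: "Newly diagnosed classic type 1 diabetes patients: N=20". There is one treatment arm.
- **Basis for the size.** The synopsis says "No real sample size calculation is done as this is an open-label pilot study just to see if the treatment is tolerable", and Section 10.2 adds "No formal power analyses is done for this pilot study".
- **Analysis.** Section 10.3 tabulates adverse events by frequency and incidence rate, broken down by body system, causality and severity: "The frequencies and incidence rates are calculated on a per patient basis". Other categorical variables get frequencies and percentages. Continuous variables get the usual summary statistics by visit.
- **Denominator.** Section 10.4 keeps withdrawn patients in the safety analysis.
- **Not stated.** The supplied text gives no confidence interval, no tolerability threshold and no account of which event rates 20 patients could rule out. The stopping text in Section 12.2 has no numerical limit.

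**The concern.** The trial's main question is answered by proportions from about 20 patients, and the plan does not say how imprecise those proportions will be. A line reading 0% or 5% for serious adverse events looks like an estimate of the rate, although the data also fit rates several times higher. Section 2.6 concedes that no pre-clinical data exist on etanercept combined with GAD immunotherapy, so these proportions will be important evidence on the combination when the next trial is designed. If they are reported without limits, a conclusion that the combination is tolerable could go further than 20 patients allow, and a larger trial in young patients could be planned on it.

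**Working it through.** The plan gives no derivation for its sample size, so there is no figure of its own to reproduce. The check asks what 20 patients can show about one event type.

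**Inputs**
- n = 20, from Section 10.1. Withdrawn patients stay in the denominator (Section 10.4).
- Confidence level: an assumption, since the plan sets none. Two-sided 95% is the main case, with one-sided 95% beside it.
- Method: exact binomial (Clopper-Pearson).

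**Zero events**
- Two-sided 95% upper limit: 1 − 0.025^(1/20) = 0.168, or 16.8%.
- One-sided 95% upper limit: 1 − 0.05^(1/20) = 0.139, or 13.9%.
- Other methods at n = 20: rule of three, 3/20 = 15.0%; Wilson, 16.1%.
- The size is only approximate. The two-sided exact limit is 1 − 0.025^(1/18) = 18.5% at n = 18 and 1 − 0.025^(1/22) = 15.4% at n = 22.

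**One or more events**

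For x events, the lower limit is the 0.025 quantile of Beta(x, 20 − x + 1) and the upper limit is the 0.975 quantile of Beta(x + 1, 20 − x).

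| Patients with the event | Observed | Exact two-sided 95% interval |
|---|---|---|
| 0/20 | 0% | 0 to 16.8% |
| 1/20 | 5% | 0.1 to 24.9% |
| 2/20 | 10% | 1.2 to 31.7% |
| 3/20 | 15% | 3.2 to 37.9% |

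**How often zero is seen when the risk is real**
- True per-patient risk 5%: 0.95^20 = 35.8% chance of no event.
- True per-patient risk 10%: 0.90^20 = 12.2% chance of no event.

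An event type that truly affects one patient in twenty would therefore be absent from the tables in more than a third of such trials.

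**The case against.** The strongest reply is that this is an openly descriptive pilot. It says that no size calculation was done, sets no hypothesis or threshold, and breaks no rule of its own. The formal objective already says *evaluate*, and Section 3 repeats that verb and presents the next trial as the source of more robust information. Counts will be reported with a denominator of about 20, so any reader can work out the interval. A data safety monitoring board reviews safety throughout (Section 6.8). Section 10.3 also describes the analysis only in brief.

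Much of this stands. The missing power calculation is acceptable in a pilot, and the point is an improvement, not the correction of an error. It can only be said that intervals are absent from the text supplied. The reply does not remove the gap, however. Estimating rates is what this trial is for, and an estimate should come with its precision by a method fixed in advance. The caveat in Section 3 about not expecting convincing statistical proof sits in the sentence on immune and beta cell effects, so it does not cover tolerability.

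Three stronger readings are tempting, and the documents do not support them:
- **That the trial might report no adverse events at all and be called tolerable.** Section 9.2.1 counts any illness that develops or worsens, follow-up lasts 30 months, and Section 2.2 already records injection-site reactions. Zero is realistic only for a specific, uncommon event type. Nothing commits the sponsor to a verdict based on a zero count.
- **That withdrawals would shrink the safety denominator and widen the limits.** Section 10.4 keeps withdrawn patients in the safety analysis.
- **That the trial fails because it cannot detect serious infections at the frequency in Section 2.3** ("Serious infections affect less than 1 of 100 patients that are treated with etanercept"). The plan makes no claim to detect them, that figure comes without a treatment duration or population, and adding an interval would not change the chance of seeing such an event.

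**Conclusion.** The point holds as a low-cost improvement. The primary tolerability proportions are planned without any measure of uncertainty, and at this size the uncertainty is large: zero events of a given type in 20 patients leaves true rates up to 16.8% open (13.9% one-sided), and a single event leaves 0.1% to 24.9%.

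This rests on the 95% level, which the documents do not specify, on the exact method, and on a denominator of 20. Across the methods tried, the upper limit for zero events in 20 runs from 13.9% to 16.8%; with 18 to 22 patients the two-sided exact limit runs from 18.5% to 15.4%. The point applies to per-patient proportions. It does not touch the continuous laboratory variables, for which Section 10.3 already plans standard deviations and ranges.

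A reader might infer that the sample size is wrong or that the trial cannot meet its objective. Neither follows. The plan states no precision target that 20 patients would miss, and the formal objective is to evaluate tolerability, which a descriptive estimate with its interval does.

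**What to change.** 1. **Section 10.3.** Report an exact (Clopper-Pearson) two-sided 95% confidence interval beside the per-patient proportions with a serious adverse event, an infection, an injection-site reaction, and discontinuation of study drug because of an adverse event. The denominator is all treated patients, including those who withdraw, in line with Section 10.4. Discontinuation is not among the tolerability variables in Section 4.2.1, but Section 5.4 already requires the reasons for withdrawal to be recorded.
2. **Section 10.2.** Keep the statement that no power analysis was done. Add that, with 20 patients, observing no event of a given type excludes only true rates above about 17% (two-sided 95%).
3. **Section 3.** Replace *ensure* with *evaluate*, to match Section 4.1.

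The cost is one extra table column and two or three sentences, with no added patients, visits or samples. The drawback for the sponsor is that the stated conclusion on tolerability becomes less favourable.

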1.1 Background and Rational

The incidence of Type 1 diabetes (T1D) in children is next to Finland highest in Sweden in the world, and is increasing rapidly. T1D is by far the most common chronic, serious, life-threatening disease in our country, and tends to become an extremely serious global problem. The disease is characterized by lack of insulin. Even though several patients at diagnosis have rather impressive residual beta cell function (1) the deficiency soon becomes very pronounced and finally complete (2,3). Residual insulin secretion is of crucial importance. In rare cases the beta cell function improves so much shortly after diagnosis that glucose metabolism normalizes and no insulin is required for some time, that is the patient goes into so called complete remission (4). As long as a the patient is in a complete remission there is no need of active treatment, more than perhaps some recommendation of sound life style regarding physical exercise and diet. There are no symptoms, no acute complications and if somebody stayed in complete remission it is unlikely that such an individual would ever develop late complications. Slight abnormality of glucose or lipid metabolism might increase the risk of macrovascular complications in the same way as for individuals with chemical diabetes or impaired glucose tolerance.

Complete remission is rare, but partial remission it is not (4). During this period the child usually has near normal blood glucose values, not even mild hypoglycemia and no episodes of ketoacidosis. The quality of life is very good as the child feels well, grows normally, needs few restrictions if any with regard to food, can exercise with great variation without getting hypoglycemia, and experiences very good home blood glucose tests. Only some residual insulin secretion is enough to diminish the risk of ketoacidosis (5). Furthermore, it has been shown in the DCCT trial that even quite modest residual insulin secretion, a response to a beta cell stimulation with serum C-peptide >0.20pmol/ml, plays an important role for prevention of complications (6). This effect may be due to the fact that residual insulin secretion should reasonably make it easier to reach good blood glucose balance, but it is also possible that C-peptide per se has a physiological function. It has in fact been reported that C-peptide influences vascular permeability, decreases leakage in retinal vessel, and not least has a positive effect on nerve function (7) although the effect of C-peptide per se still is under debate.

1.1.1 Factors influencing the natural course

At diagnosis of T1D it has been claimed that 70-90% of the beta cells in pancreas have been destroyed. However, the proof for this is scarce, and it may well be that the main problem is deterioration of function. Furthermore there is great difference between patients, as some have quite good residual insulin secretion and others have not. Shortly after diagnosis, especially when an active insulin treatment is given, there is an increase of C-peptide production, and at the same time an improvement of insulin sensitivity. Good metabolic control seems to improve the milieu and metabolism for the beta cells and the beta cell function is preserved, which in turn contributes to better metabolic control, and vice versa. The intensity of the autoimmune process plays a role, and it seems evident that children have a more aggressive immune process than adults with T1D, but it is still difficult to predict the course. Some studies have suggested that high concentrations of auto-antibodies are followed by a more rapid loss of insulin secretion, while others have not found such a relationship, or even the opposite. No special signs of cell-mediated immunity have so far been proven to predict beta cell loss but our own studies have shown that disease process is related to a T-helper-1 (Th-1) deviation of the immune system with increase of certain cytokines such as IFNg and decrease of IL-10, IL-13.

Interventions that may preserve beta cell function.

Active insulin treatment during the first period of the disease prolonged the partial remission long time ago, and this finding could be confirmed and validated by improved residual insulin secretion (2). Intensified treatment seems to improve residual beta cell function at least for some time (8), but it may also have long-term positive effects (9). Active treatment has been shown not only to prevent or postpone diabetes in experimental animals, but studies have indicated that such treatment could prevent diabetes in high risk individuals (10). However, when tried at a larger scale in the Diabetes Prevention Trial, parenteral insulin treatment did not prevent diabetes (11). Oral treatment with insulin might have an effect (12) and therefore further studies are needed.

